12.2.2 Safety variables

Analysis of time from first dose of study medication to each of the following endpoints will be performed

- the first TIMI major bleeding event (primary safety variable)
- the first TIMI major or minor bleeding event
- the first PLATO major bleeding event
- discontinuation of study medication due to any major bleeding event

The assessment of time to bleeding will focus on the items above but will also include analysis of time to first event for additional categories of bleeding according to the TIMI, PLATO, BARC and ISTH definitions. Treatment groups will be compared using the Cox proportional hazards model with a factor for treatment group. Kaplan-Meier estimates of the cumulative incidence of each event will be calculated and plotted and 95% confidence intervals for the hazard ratios presented. The safety assessment will also include analysis of total major bleeding events, fatal bleeding events, fatal or life threatening bleeding events, combined major and minor bleeding events separately. Exploration of potential risk factors for bleeding events, including subgroups and use of concomitant antithrombotic therapy, will be performed.

Bleeding events will be analyzed according to TIMI and PLATO bleeding definitions adjudicated by the CEC (see the CEC charter). BARC and ISTH bleeding profiles will be captured for each patient where appropriate but will not be formally adjudicated (Mehran 2011, Schulman 2005).

Non-serious AEs of interest, DAEs as well as SAEs will also be evaluated. MedDRA will be used for the coding and classification of AEs and SAEs in the database. AEs will be summarised by system organ class and preferred term using MedDRA. Summaries will be presented by treatment group using descriptive statistics. All AEs relating to bleeding will be summarised separately and the total number of bleeding events will be assessed. Exploration of potential risk factors for AEs that are increased with ticagrelor dosing may be done.

12.2.3 Interim analyses

The independent DMC will perform an interim analysis for potential early termination of the study for overwhelming efficacy, additional analyses may occur as defined in the DMC Charter. This interim analysis is planned after approximately 798 primary events have been adjudicated. A one-sided significance level of 0.001 (ie approximately 3 standard errors) will be used as criterion to consider stopping the study for overwhelming benefit of ticagrelor over clopidogrel. For early stopping the one-sided p-value must be less than 0.001 for the primarv composite, as well as for CV Death alone. A one-sided significance level of 0.001 will be applied at each efficacy interim analysis. The Haybittle-Peto alpha spending function will govern the statistical testing at the final analysis to ensure an overall Type I error of 5% (East 5.2). If the planned interim analysis is performed when at least half of the total number of primary events have occurred and there are no additional interim analyses for efficacy, the significance level at the final analysis is at most 0.0494 (two-sided). If there are deviations from this plan the significance level at the final analysis will be adjusted according to the Haybittle-Peto alpha spending function. If the study is stopped at an efficacy interim analysis after having met the criteria for the primary composite endpoint and CV death, the testing of the remaining secondary endpoints will continue at the one-sided significance level 0.001. First CV death+MI+ischemic stroke+ALI will be tested and therafter variables 3-8 in the sequence described in Section 12.2.1. There will be no futility stopping rule.

The DMC charter contains more information about the DMC procedures. A copy of the treatment codes will be made available to the statistician on the DMC. The Executive Committee and AstraZeneca will not be made aware of the treatment codes until after clean file and database lock are declared. Similarly, all summary output reviewed at each DMC meeting will be held in confidence by the DMC members until the end of the study when clean file and database lock are declared. Further details are given in the DMC charter.

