12.2 Methods of statistical analyses

12.2.1 Efficacy analysis

All efficacy analyses will be based on the intent-to-treat principle using the FAS, including only events adjudicated by the CEC. Investigators are instructed to report all suspected endpoints in the eCRF, even those that may not meet strict endpoint definitions, to ensure all potential events are reviewed and adjudicated by the CEC. The time from randomisation to the first occurrence of any event in the given endpoint will be compared using the Cox proportional hazards model with a factor for treatment group. The p-value, HR, and 95% confidence interval will be reported. No multiplicity adjustment will be made to the confidence intervals, as they will be interpreted descriptively and used as measures of precision. Kaplan-Meier estimates of the cumulative risk of each composite endpoint and its individual components will be calculated and plotted.

Primary efficacy variable:

The primary analysis will compare the time from randomisation to the first occurrence of any event in the composite endpoint CV death, MI and ischaemic stroke. Refer to Appendix E for definitions of CV death, MI and ischaemic stroke.

The null hypothesis will be that the risk/hazard of an event on ticagrelor is equal to the corresponding risk/hazard on clopidogrel:

 H_0 : HR (ticagrelor divided by clopidogrel) = 1

The alternative hypothesis will be that the HR is greater, or less than 1:

H₁: HR \neq 1

The hypothesis will be tested at 4.94% two-sided significance level to account for the single planned interim analysis with the overall type I error preserved at 5%. If the DMC conducts additional interim analyses of the primary outcome, these levels will be adjusted accordingly using the alpha spending function. For definition of the significance level of the final analysis, see Section 12.2.3.

The HR and 95% confidence interval will be reported. Kaplan Meier estimates of the cumulative incidence to the first occurrence of any event in the composite endpoint will be calculated and plotted, as will the cumulative risk to the first occurrence of each component separately. The contribution of each component of the primary composite efficacy endpoint to the overall treatment effect will be examined.

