12.3 Determination of sample size

Based on clinical studies and epidemiological information, the event rate for the composite of CV death, MI and ischaemic stroke was estimated to be 7% per year in a population consisting of a spectrum of symptomatic PAD patients.

In the PLATO study a 16% RRR and 1.9% ARR (ticagrelor 9.8%, clopidogrel 11.7%) at one year were observed for the endpoint of CV death, MI and stroke. In the PAD subgroup in PLATO (data on file), a similar RRR of 15% was observed at higher absolute frequencies, ARR= 2.6% (18.0% vs. 20.6%). The RRR for ticagrelor versus clopidogrel in PLATO demonstrated consistency across multiple subgroups and consistency over time during the course of PLATO. In addition, results for the endpoint CV death, MI, and ischaemic stroke were similar to those obtained for CV death, MI, and stroke. With these considerations in mind a 15% RRR, which with 7% event rate corresponds to a 1.02% ARR per year, was assumed for the primary endpoint of CV death, MI, and ischaemic stroke of this study.

Assuming a 7% annual reference event rate and a HR of 0.85 over 18 months accrual period and anticipated 18 months of minimum follow-up, randomisation of approximately 11,500 patients **was** expected to yield 1596 primary endpoint events, which provide 90% power at a 4.94% significance level. Randomising an additional 2000 patients (i.e. target randomization approximately 13500 patients) would allow us to accrue the required 1596 primary endpoint events in approximately the above time frame if the clopidogrel event rate is 6%. For definition of the significance level at the final analysis, see Section 12.2.3. The sample size

was based on a test using the logrank statistic and was calculated using nQuery Advisor^{®1} 7.0.

The observed aggregate event rate is currently estimated to be approximately 4.1%, and to conclude the study in a timely manner with maintained data quality, the number of targeted primary events will be reduced to a minimum of 1364, which will provide 85% power at 4.94% significance level. The sample size was again based on a test using the logrank statistic and was calculated using nQuery Advisor 7.0.

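### Section 12.2.3 gives 0.0494 as the most the final significance level can be for an interim at or beyond half the events; under the stated rule it is the least

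*Protocol*

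**What the plan says.** Section 12.2.3 of the protocol sets the interim rule. On timing: "This interim analysis is planned after approximately 798 primary events have been adjudicated". On the boundary: "A one-sided significance level of 0.001 will be applied at each efficacy interim analysis". The Haybittle-Peto function "will govern the statistical testing at the final analysis to ensure an overall Type I error of 5% (East 5.2"). Stopping also needs the same result on CV death, not on the primary composite alone.

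The sentence at issue has a condition and a conclusion. The condition is: "If the planned interim analysis is performed when at least half of the total number of primary events have occurred", with no further efficacy interims. The conclusion is: "the significance level at the final analysis is at most 0.0494 (two-sided"). Departures from this plan lead to an adjustment by the same function.

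Section 12.2.1 then uses a fixed level: "The hypothesis will be tested at 4.94% two-sided significance level to account for the single planned interim analysis". The same 4.94% governs each step of the secondary hierarchy. It also appears in the synopsis and in both power statements of section 12.3. Sections 12.2.1 and 12.3 send the reader to 12.2.3 for the definition of the final level.

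Section 12.3 records the amendment: "the number of targeted primary events will be reduced to a minimum of 1364". The previous target was 1596. The interim stays at about 798 events.

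**The concern.** With a fixed interim boundary, a later interim is more strongly correlated with the final statistic. More of the trials that cross at the interim would also have crossed at the end, so the interim costs less and more of the 5% is left for the final test. The permissible final level therefore rises with the information fraction. For an interim at half the events or later, the value at exactly half is a floor. Section 12.2.3 states it as a ceiling.

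The figure also belongs to the original target, of which 798 was exactly half. With 1364 events as the target it is more than half, and the level that the method yields is no longer 0.0494.

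At stake is whether the section that defines the decision threshold for the primary test and the hierarchy describes its own method correctly. As written, it gives an upper bound that the method does not produce, while the sections that rely on it use one fixed value.

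**Working it through.** **Inputs, all from the protocol.** Overall two-sided error 5%, interim boundary one-sided 0.001 and interim at about 798 events (12.2.3); original target 1596 and amended target 1364, HR 0.85 (12.3); 1:1 allocation (3.1).

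**Method.** Let Z1 and Z2 be the interim and final statistics. Under the null they are bivariate normal with correlation √t, where t is interim events divided by final events. The interim critical value for one-sided 0.001 is 3.0902. Solve for c in

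P(|Z1| > 3.0902 or |Z2| > c) = 0.05,

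and report the final two-sided level 2·[1 − Φ(c)].

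**Reproducing the stated figure.** t = 798/1596 = 0.50 and √t = 0.7071. The solution is c = 1.9649, a level of 0.04943. This is the protocol's 0.0494.

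**Amended target.** t = 798/1364 = 0.585 and √t = 0.7649. The solution is c = 1.9631, a level of 0.04964, or about 0.0496.

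**Direction of the inequality.**

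| t | final two-sided level |
|---|---|
| 0.40 | 0.0492 |
| 0.50 | 0.0494 |
| 0.585 | 0.0496 |
| 0.70 | 0.0499 |
| 0.80 | 0.0500 |

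The level rises throughout. It is at most 0.0494 only for an interim at or before half the events, the opposite of the stated condition.

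**Sensitivity to convention.** With an interim boundary of exactly z = 3, the level is 0.0491 at t = 0.50 and 0.0494 at t = 0.585. With only the benefit side tested at the interim and a two-sided final test, it is 0.0497 and 0.0498. It rises with t in each case. Only the one-sided 0.001 boundary applied on both sides reproduces 0.0494 at t = 0.50.

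**Sensitivity to the final count.** With 798 interim events, the level is 0.0496 at 1364 final events, 0.0496 at 1450 (0.04956), 0.0495 at 1500 and 0.0494 at 1596.

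**Error if 0.0494 is kept.** At t = 0.585, with c = 1.9651 (two-sided 0.0494), the overall error is 0.04977, below 5%. At t = 0.40 the same level would give 0.0502, slightly above 5%.

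**Power (Schoenfeld).** Power = Φ(|ln 0.85|·√D/2 − z), where D is the number of events and z the final critical value.
- D = 1596, level 0.0494: Φ(3.2463 − 1.9651) = 89.99%.
- D = 1364, level 0.0494: Φ(3.0011 − 1.9651) = 84.99%.
- D = 1364, level 0.0496: Φ(3.0011 − 1.9634) = 85.03%.

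The protocol's 90% and 85% are both reproduced.

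**The case against.** The strongest defence is that the operative threshold is clear and safe. The synopsis and sections 12.2.1 and 12.3 all use 4.94%. At any interim fraction of one half or more, that level keeps overall error at or below 5%. A prespecified level slightly under the permissible maximum is legitimate, and the sentence could be read as a promise never to use more than 0.0494. The validity argument stands in full. The reading as a promise is weaker: the sentence follows directly from the statement that the spending function governs the final test, and it reads as what that function yields. Nothing in the protocol calls 0.0494 a deliberate conservative choice.

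A reader might go further and infer that 4.94% is now an error and that 0.0496 should replace it everywhere. The documents do not support that. The interim count is approximate and 1364 is a minimum, so the exact level cannot be fixed in advance. A final count well above 1364 would make 0.0496 slightly too high: at 1500 events the permissible level is 0.04951. Nor does 0.0496, or the benefit-side 0.0498, reflect the added CV-death condition, under which less error is spent at the interim. The protocol's gloss of the boundary as about 3 standard errors would alone move the figure back to 0.0494 at 798/1364.

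A reader might also infer that type I error is inflated or the trial underpowered. Neither is so, as the working shows.

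The clause on departures from plan does not repair the sentence. An interim at 58.5% meets the condition of at least half, so that clause is not triggered.

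**Conclusion.** The sentence in 12.2.3 is wrong as written: its inequality is reversed. The direction does not depend on the convention used for the boundary. The 4.94% level comes from the original 50% fraction. At 58.5% it remains a valid, slightly conservative threshold.

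The size is small. The gap is 0.0002 in the final level (0.0494 against about 0.0496), overall error is about 0.0498 instead of 0.0500, and power differs by about 0.04 percentage points. Only a final p-value inside that 0.0002 window would be judged differently.

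These figures assume a one-sided 0.001 boundary on both sides, exactly 798 and 1364 events, a single efficacy interim and no allowance for the CV-death condition.

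**What to change.** Correct 12.2.3 to say that, for a single interim at or beyond half of the final number of primary events, the Haybittle-Peto level for the final test is no lower than 0.0494. That sentence alone would leave the threshold open upwards, so follow it with one definite operative rule:

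- compute the final level from the actual interim and final event counts, giving about 0.0496 at 798/1364 as an illustration and not as a fixed value; or
- state that 0.0494 is kept as a fixed conservative level whenever the interim falls at or beyond half the events.

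Then align the synopsis, section 12.2.1 (the primary test and the cut-off in the hierarchy) and section 12.3 with the rule chosen. The second option changes no number. Either way the cost is wording only, with no effect on events or timeline.

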12.2.4 Censoring

The Executive Committee will monitor the accrual of the number of primary events and when appropriate predict and define a primary analysis censoring date at which time the pre-defined target number of events for the primary composite endpoint are expected to have occurred.

The primary analysis censoring date will be the common date at which all patients who are event free for the given endpoint and have not withdrawn consent for participating in the study will be censored in efficacy time-to-event analyses. Events that occur after the primary analysis censoring date but before the ESTV will also be collected and adjudicated. These events may be included in sensitivity analyses but not in the primary analysis.

Patients who have not had the event(s) in question will be censored at the earlier of (1) the primary analysis censoring date and (2) the last study contact when all components of the endpoint in question were assessed. In the analysis of CV death and composites including CV death censoring will occur at the earliest of (1), (2) and the date of death from non-cardiovascular causes. For endpoints not including death, all deaths are censoring events.

Complete endpoint information will be pursued with every effort for all patients regardless of their study medication status, unless they exercise their right to withdraw consent. Patients who have a non-fatal event will continue study follow-up. For patients who withdraw consent and for whom only vital status (known to be alive at study closure, or date of death) may be obtained from public records, the occurrence of all components of the primary endpoint cannot be assessed. Thus the primary endpoint and its components ischaemic stroke, MI, and CV death will be censored at the time of consent withdrawal for those patients who withdraw consent and for whom only vital status is known from public records. However, the determination of all-cause mortality as a sole outcome event will utilise all publicly known mortality data, even that extending beyond date of consent withdrawal. The vital status information will be included in the analysis of all-cause mortality as a single secondary endpoint, in sensitivity analyses and tabulations.

Similarly, complete information on the primary endpoint may not be obtained for patients who are lost to follow-up (LTFU). Any such patient will be censored in the analysis of the primary composite endpoint at the last contact where all elements of the endpoint were assessed. A patient will not be recorded as LTFU until the end of the study, after every allowable effort to get in contact has been made. Hence, it is anticipated that the number of patients LTFU will be limited.

12.3 Determination of sample size

Based on clinical studies and epidemiological information, the event rate for the composite of CV death, MI and ischaemic stroke was estimated to be 7% per year in a population consisting of a spectrum of symptomatic PAD patients.

In the PLATO study a 16% RRR and 1.9% ARR (ticagrelor 9.8%, clopidogrel 11.7%) at one year were observed for the endpoint of CV death, MI and stroke. In the PAD subgroup in PLATO (data on file), a similar RRR of 15% was observed at higher absolute frequencies, ARR= 2.6% (18.0% vs. 20.6%). The RRR for ticagrelor versus clopidogrel in PLATO demonstrated consistency across multiple subgroups and consistency over time during the course of PLATO. In addition, results for the endpoint CV death, MI, and ischaemic stroke were similar to those obtained for CV death, MI, and stroke. With these considerations in mind a 15% RRR, which with 7% event rate corresponds to a 1.02% ARR per year, was assumed for the primary endpoint of CV death, MI, and ischaemic stroke of this study.

Assuming a 7% annual reference event rate and a HR of 0.85 over 18 months accrual period and anticipated 18 months of minimum follow-up, randomisation of approximately 11,500 patients **was** expected to yield 1596 primary endpoint events, which provide 90% power at a 4.94% significance level. Randomising an additional 2000 patients (i.e. target randomization approximately 13500 patients) would allow us to accrue the required 1596 primary endpoint events in approximately the above time frame if the clopidogrel event rate is 6%. For definition of the significance level at the final analysis, see Section 12.2.3. The sample size

was based on a test using the logrank statistic and was calculated using nQuery Advisor^{®1} 7.0.

The observed aggregate event rate is currently estimated to be approximately 4.1%, and to conclude the study in a timely manner with maintained data quality, the number of targeted primary events will be reduced to a minimum of 1364, which will provide 85% power at 4.94% significance level. The sample size was again based on a test using the logrank statistic and was calculated using nQuery Advisor 7.0.

12.4 Independent Data monitoring committees

12.4.1 Clinical Event Adjudication Committee

An independent, blinded Clinical Event Adjudication Committee (CEC) will be appointed and will report to the DMC and Executive Committee.

The CEC will adjudicate all primary and secondary endpoints and bleeding events with the exception of occurrence of revascularization. The CEC charter details the precise responsibilities and procedures applicable for the CEC.

12.4.2 Data Monitoring Committee

An independent Data Monitoring Committee (DMC) will be appointed and will report to the Executive Committee.

The DMC will be responsible for safeguarding the interests of the patients in the outcome study by assessing the safety of the intervention during the study, and for reviewing the overall conduct of the clinical study. The DMC will have access to the individual treatment codes and will be able to merge these with the collected study data while the study is ongoing.

The DMC charter will be prepared to detail precise roles and responsibilities and procedures to ensure maintenance of the blinding and integrity of the study in the review of accumulating data and interactions with the Executive Committee

13.2 Overdose

An overdose of study medication is defined as intake of more than 4 yellow ticagrelor/placebo tablets or more than twice the prescribed dose of pink clopidogrel/placebo tablets a day.

In the event of an overdose of study medication ascertain the time and extent of the overdose regardless of severity. Determine the causative circumstance and whether haemorrhagic or toxic complications have occurred or are likely to do so. Depending on these facts it has to be decided if the patient should be hospitalised for observation or not. Bleeding is one of the most likely pharmacological effects of excessive ticagrelor dosing, and appropriate supportive measures such as volume replacement, local haemostatic measures, and decompression or drainage may be required depending on the extent of bleeding or volume of blood lost. Patients with overdose-related bleeding should be cautioned to avoid unnecessary activity, mechanical tissue stress, and minor trauma for at least 24 hours after the bleeding has stopped. For other symptoms that can be expected after an overdose of ticagrelor and additional information see the IB.

An overdose with associated AEs of interest or SAEs should be recorded. The SAE diagnosis/symptoms should be recorded on the relevant forms in the eCRF.

• An overdose without associated symptoms is only reported on the Overdose eCRF module.

If an overdose on an AstraZeneca study medication occurs in the course of the study, then investigators or other centre personnel inform appropriate AstraZeneca representatives within 1 day, ie, immediately but no later than 24 hours of when he or she becomes aware of it.

The designated AstraZeneca representative works with the investigator to ensure that all relevant information is provided to the AstraZeneca Patient Safety data entry centre.

For overdoses associated with SAE, standard reporting timelines apply, see Section 6.4.4. For other overdoses, reporting should be done within 5 days.

